### **6.3 Interim Analyses and Data Monitoring**

There will be no interim analysis or formal data monitoring during this study.

### **6.4 Multiple Comparisons/Multiplicity**

There will be no multiple comparison/multiplicity for this study.

### **6.5 Examination of Subgroups**

To examine potential differences in the outcomes by the subgroups as below, the following data will be summarized separately by the subgroups: SSF, Relative change (%) from baseline in SSF, responders, adverse events, and PCS laboratory parameters.

#### **Demographic subgroups**

- Age (<18, 18-65, >65 years old)
- Gender (Male, Female)
- Race (White, Black or African American, Asian, Other)

#### **Baseline AEDs subgroups**

An AED is considered to be used at baseline if it started at any time prior to the first dose of study treatment and continued into the titration period from protocol 093-045 or 093-045. Subjects may appear in multiple AED use subgroups.

- Number of baseline AEDs (0, 1, 2, or more AEDs)
- Baseline AEDs
  - Use of carbamazepine as baseline AED (yes/no)
  - Use of oxcarbazepine as baseline AED (yes/no)
  - Use of carbamazepine or oxcarbazepine as baseline AED (yes/no)
  - Use of lamotrigine as baseline AED (yes/no)

- Additional individual baseline AEDs that occur in  $\geq 15\%$  of the subjects (namely, levetiracetam, and valproic acid)

### **Seizure subgroups**

Seizure type (simple partial, complex partial, partial evolving to secondarily generalized seizures)

### **Actual Monotherapy Used subgroup**

The subjects who started on actual monotherapy (i.e. 10 weeks double-blind monotherapy from protocol 093-045 or 093-046), entered this study and did not add any non-rescue AED during the study participation will be defined as Actual Monotherapy Used subgroup.

For those subjects, the following data including ESL exposure and compliance, concomitant medication, SSF, relative (%) change from baseline in SSF, responders, TEAE, SAE, Death, TEAE leading to discontinuation, and minimum post-dose sodium level change from baseline will be summarized.

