## 3. Study design

### 3.1. General Description

This study is a long-term, multicenter, open-label, safety extension study in male and female subjects (aged 16 to 70 years, inclusive) with partial onset seizures who have just completed, discontinued, or exited the 18-week treatment phase of Protocols 093-045 or 093-046. The initial study duration is 1-Year Open-Label Period with the option of continuing study drug treatment Post-1-Year Open-Label Period until a subject discontinues study, the study drug becomes clinically available in the subject's locale, or the sponsor terminates the study drug clinical development program.

This study will evaluate the safety and maintenance of effect of long-term eslicarbazepine acetate treatment at flexible doses in the range of 800 mg to 2400 mg once-a-day (QD) over a 1-Year Open-Label Period and a Post-1-Year Open-Label Period.

[figure not shown]

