Subjects who enter the present study will receive a starting dose of 1600 mg QD of eslicarbazepine acetate, orally for 1 week at the start of the 1-Year Open-Label Period. The starting dose for subjects who had a dose reduction during participation in studies 093-045 or 093-046 will be 1200 mg and not 1600 mg. At the end of this 1-week period, subjects will be allowed to continue at this dose or at the discretion of the Investigator, increase, or decrease dose as necessary for efficacy or tolerability reasons. There is no limit on the number of dose increments or reductions during the study, however, all dose increases or reductions should occur in steps of 400 mg and a minimum of 1 week must pass between one dose change and the next. Dose reductions of more than 400 mg are allowed at the discretion of the Investigator for a documented safety reason. The maximum allowed dose of eslicarbazepine acetate is 2400 mg QD and the minimum allowed dose is 800 mg QD in this study. Subjects who continue into the Post-1-Year Open-Label Period part of the study will continue to receive the same dose of study drug that they received at Visit 7 (end of 1-Year Open-Label Period of treatment). The same dosing rules as in the 1-Year Open-Label Period part of the study are applicable in the Post-1-Year Open-Label Period part. Subjects with a clinically significant increase in seizure frequency, duration, or severity, who have not responded to or did not tolerate an increase in dose of study drug, may be started on an additional antiepileptic drug (AED) during both the 1-Year Open-Label Period and Post-1-Year Open-Label Period parts of the study. A maximum of two additional AEDs to control seizures will be allowed, however oxcarbazepine will not be allowed. If, after the addition of the second additional AED, the subject experiences an adverse event, the dose of eslicarbazepine acetate should be reduced before changing the dose of the concomitant AED. In addition, for subjects with a vagal nerve stimulator (VNS), the device setting may be changed as needed.

Subjects who require doses outside of the 800 mg QD to 2400 mg QD range or more than 2 additional AEDs during the 1-Year Open-Label Period or Post-1-Year Open-Label Period parts of the study will be discontinued from study participation.

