### 3.2. Study Schematic

EOS=end of study; ET=early termination; M=month; V=visit.

\*Corresponds to Visit 9 in Protocols 093-045 and 093-046. \*\*1200 mg QD for subjects who had a dose reduction while participating in Protocols 093-045 or 093-046.

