### 5.2.2. 1-Year Open-Label Period Efficacy Endpoints

#### 1. Time on eslicarbazepine acetate monotherapy

Time on eslicarbazepine acetate monotherapy during 1-Year Open-Label Period will be calculated from the date of the first eslicarbazepine acetate monotherapy dose in protocol 093-045 or 093-046 (Visit 6/Week 8) to the last known dose of eslicarbazepine acetate monotherapy during 1-Year Open-Label Period as follows;

- a. For a subject who added a non-rescue AED during 1-Year Open-Label Period, Time on Monotherapy during 1-Year Open-Label Period is calculated as the date of start a non-rescue AED during 1 Year Open-Label Period minus the date of the first monotherapy dose in protocol 093-045 or 093-046.
- b. For a subject who completed the 1-Year Open-Label Period, and did not add any non-rescue AED since the date of the first monotherapy dose in protocol 093-045 or 093-046, Time on Monotherapy during 1-Year Open-Label Period is calculated as the date of the last known dose during 1-Year Open-Label Period, minus the date of the first monotherapy dose in protocol 093-045 or 093-046, plus 1.
- c. For a subject who did not complete the 1-Year Open-Label Period, and did not add any non-rescue AED since the date of the first monotherapy dose in protocol 093-045 or 093-046, Time on Monotherapy during 1-Year Open-

Label Period is calculated as the date of the known dose before the withdrawal during 1-Year Open-Label Period, minus the date of the first monotherapy dose in protocol 093-045 or 093-046, plus 1.

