### **Time on eslicarbazepine acetate monotherapy**

Kaplan Meier methods will be used to estimate the median time (and 95% CI) on eslicarbazepine acetate monotherapy for both 1-Year Open-Label Period and Post-1-Year Open-Label Period.

For the 1-Year Open-Label Period, time on monotherapy as defined in Section 5.2.2 will be used for analysis. Subjects who were still taking only eslicarbazepine acetate as monotherapy at the end of the 1-Year Open-Label Period of study will be censored at the last dose of the 1-Year Open-Label Period. Subjects who withdrew during the 1-Year Open-Label Period will also be censored at the time of the last known dose before the withdrawal. Subject who added a non-rescue AED will be an event on the date of the start AED during 1-Year Open-Label Period.

For the Post-1-Year Open-Label Period, time on monotherapy as defined in Section 5.2.3 will be used for analysis. Subjects who were still taking only eslicarbazepine acetate as monotherapy at the end of the Post-1-Year Open-Label Period will be censored at the last dose of the Post-1-Year Open-Label Period. Subjects who withdrew during the Post-1-Year Open-Label Period will also be censored at the time of the last known dose before the withdrawal. Subject who added a non-rescue AED will be an event on the date of the start AED during Post-1-Year Open-Label Period.

Subjects who never started the monotherapy treatment period in protocol 093-045 or 093-046 will not be included in this analysis. Change in dosage levels from protocol 093-045 or 093-046, dosage changes during protocol 093-050, and the time gap between the parent studies and the extension study will be ignored.

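### The Actual Monotherapy Used rule checks only for AEDs added during 093-050, so as worded it can admit a subject who entered on an AED restarted in the parent study

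*SAP*

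**What the plan says.** SAP section 6.5 (Actual Monotherapy Used subgroup) sets three conditions. The subject must have "started on actual monotherapy (i.e. 10 weeks double-blind monotherapy from protocol 093-045 or 093-046"), must have entered this study, and must have added no non-rescue AED while participating. The last two conditions and the label read: "entered this study and did not add any non-rescue AED during the study participation will be defined as Actual Monotherapy Used subgroup".

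The subgroup has its own summaries of exposure and compliance, concomitant medication, SSF, relative change in SSF, responders, TEAEs, SAEs, deaths, discontinuations due to TEAEs, and sodium. Section 7.7.2 repeats the sodium categories for it, and section 7.2 reports its size.

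The time-on-monotherapy endpoint uses a different look-back. In section 5.2.2 item 1, rules (b) and (c) apply to a subject who "did not add any non-rescue AED since the date of the first monotherapy dose in protocol 093-045 or 093-046". Section 5.2.3 item 3 uses the same condition for the post-1-year period. The clock for that endpoint runs "from the date of the first eslicarbazepine acetate monotherapy dose in protocol 093-045 or 093-046 (Visit 6/Week 8").

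On entry, section 3.1 admits subjects "who have just completed, discontinued, or exited the 18-week treatment phase of Protocols 093-045 or 093-046". A footnote to the schematic in section 3.2 reads "Corresponds to Visit 9 in Protocols 093-045 and 093-046". For the time-on-monotherapy analysis, section 7.6 says that "the time gap between the parent studies and the extension study will be ignored".

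**The concern.** The subgroup's name tells the reader that its members took eslicarbazepine acetate alone. The rule does not require a subject to be on monotherapy at Visit 1, and it does not look at AEDs started between the first parent monotherapy dose and Visit 1. An AED restarted in that interval and carried into 093-050 is not one added during 093-050, so it does not disqualify.

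The parent studies are monotherapy trials, so these are the tables a reader would turn to for long-term monotherapy experience. If subjects on a second AED are among them, seizure control, adverse events and sodium changes that occurred on combination treatment would be reported as monotherapy results. The direction of any resulting bias cannot be predicted.

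**Working it through.** **The window.** Inputs: an 18-week parent treatment phase (SAP section 3.1), and monotherapy starting at Visit 6/Week 8 (section 5.2.2 item 1). 18 − 8 = 10 weeks, which reproduces the length of the double-blind monotherapy phase given in section 6.5. An AED restart is therefore unscreened by section 6.5 for up to 10 weeks, plus any gap between the parent study and the extension.

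**A test case.** Suppose a subject starts monotherapy at Week 8, restarts a non-rescue AED at Week 12, exits the parent study, enters 093-050 still taking that AED, and adds nothing more.

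| Rule | Question | Answer |
|---|---|---|
| 6.5 | Started parent monotherapy? | Yes |
| 6.5 | Entered 093-050? | Yes |
| 6.5 | Added a non-rescue AED during 093-050? | No, so **in** the subgroup |
| 5.2.2 item 1 (b), (c) | No non-rescue AED added since the first parent monotherapy dose? | Condition **not met** |
| 5.2.2 item 1 (a) | Non-rescue AED started in the 1-Year Period? | No, so (a) does not apply |

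Section 6.5 includes this subject. Section 5.2.2 does not treat the subject as free of added AEDs, and none of its three rules gives the subject a time on monotherapy. The subgroup and the endpoint therefore use different look-backs for the same idea.

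**Can the case arise under the entry rule?** Section 3.1 does not restrict entry to parent completers, and section 7.6 acknowledges a time gap before the extension. Neither shows that such a subject exists, but neither rules one out.

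**How many subjects?** The documents give no count of AED restarts in the parent studies, so the number cannot be computed. As pure illustration, let *a* be the share of parent monotherapy starters who enter on a restarted AED and add none, and let *b* be the share of the rest who add an AED in 093-050. The share of the subgroup that entered on a second AED is a / [a + (1 − a)(1 − b)].

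- a = 0: 0 for any b below 1.
- a = 0.05: 0.05 / (0.05 + 0.95 × 0.90) = 5.5% at b = 0.10, and 0.05 / (0.05 + 0.95 × 0.70) = 7.0% at b = 0.30.
- a = 0.20: 0.20 / (0.20 + 0.80 × 0.90) = 21.7% at b = 0.10, and 0.20 / (0.20 + 0.80 × 0.70) = 26.3% at b = 0.30.

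Both *a* and *b* are assumed, with nothing in the documents to anchor them. The results restate those assumptions and are not estimates for this study.

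**The case against.** **The case may never occur.** Whether a subject could restart an AED after Week 8 and enter 093-050 on it depends on the parent protocols. The design also suggests near-continuous rollover: subjects have only just left the parent study, and parent Visit 9 results serve for Visit 1 (SAP section 5.1, note d). An AED started at or after parent exit could then carry a date on or after Visit 1 and would disqualify under section 6.5 as written. This limits the likely number and stands as a caution about size. It does not close the gap, because a restart before exit is still unscreened and section 7.6 allows for a time gap.

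**The wording can be read differently.** Participation could be taken to cover the parent study as well, since section 3.1 also uses the word for 093-045 and 093-046, and the mention of 10 weeks could be taken to mean completed monotherapy. Both readings are weaker than the plain text. The phrase follows directly on entry to this study, and section 3.1 uses the same term for removal from 093-050 ("will be discontinued from study participation"). The condition is that monotherapy was started, and starting is also the threshold in section 7.6. If one of these other readings is intended, two programmers could still build different subgroups.

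**The AED would be visible.** The subgroup's own outputs include concomitant medication. Section 5.3.2 counts any medication present on or after first dose, and section 7.7.7 tabulates AEDs separately. This is correct, and the problem would not be hidden. Showing the AED does not, however, take the subject out of the SSF, responder, TEAE or sodium summaries.

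**Stronger readings a reader might infer.** One is that such subjects are on polytherapy throughout 093-050. That holds only if the restarted AED is continued. Another is that section 5.2.2 declares them not to be on monotherapy. It does not: rules (a) to (c) are duration formulas, and they leave the subject unassigned.

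**Conclusion.** The point holds as a defect in a definition. As worded, section 6.5 can place a subject in the Actual Monotherapy Used subgroup while that subject is taking a restarted non-rescue AED, for as long as that AED continues. It is also inconsistent with the look-back in sections 5.2.2 and 5.2.3.

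The conclusion rests on reading study participation as participation in 093-050, and on started as not meaning completed. The documents do not show that anyone is misclassified: the number may be small or zero, and no percentage can be supported.

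The consequence is confined to descriptive subgroup tables in an open-label extension. The main safety and efficacy summaries use the ITT population (section 7.1) and are unaffected. The change is still worth making, because every summary for this subgroup inherits its membership rule.

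**What to change.** In section 6.5, define the subgroup as subjects who started the parent monotherapy phase, entered 093-050, and had no non-rescue AED added from the first parent monotherapy dose to the end of 093-050 participation. State explicitly that a non-rescue AED ongoing at Visit 1 disqualifies.

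The first part carries over the look-back of sections 5.2.2 item 1 and 5.2.3 item 3. The explicit statement about Visit 1 goes somewhat further than those sections and should be recognised as an addition.

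The cost is a short edit to the SAP and one programming condition on AED dates, which the time-on-monotherapy endpoint already needs. The subgroup may become slightly smaller. If no subject entered on a restarted AED and none had added one between the first parent monotherapy dose and Visit 1, the tables do not change.

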## **7. Statistical Analysis**

### **7.1 Analysis Populations**

The intent-to-treat (ITT) population will consist of all subjects who have taken any open-label study medication. The ITT population will be used for all safety and all efficacy analyses.

The per-protocol (PP) population will consist of all subjects in the ITT population who did not have any important protocol deviations. The per-protocol population will be used in an additional analysis of the efficacy endpoints and subject demographics and baseline characteristics.

### **7.2 Disposition of Subjects**

The number and percentage of subjects who entered 1-Year Open-Label Period, who completed the 1-Year Open-Label Period, who discontinued during 1-year Open-Label Period (including reasons for discontinuations), who completed 1-Year Open-Label period but did not enter the Post-1-Year Open-Label Period, entered Post-1-Year Open-Label Period, and discontinued early (including reasons for discontinuations) for Post-1-Year Open-Label Period, and who completed Post-1-Year Open-Label Period will be summarized. The number and percentage of subjects who were in actual monotherapy used subgroup and PP population will be also summarized respectively.

Subject disposition will be summarized for the ITT population.

Listing of subject disposition will be provided.

### 7.3 Protocol Deviations

Prior to database lock, important protocol deviations (IPDs) will be identified in a review of all protocol deviations reported. Possible IPDs will include, but may not be limited to, subjects who:

- Did not meet inclusion/exclusion criteria or eligibility was not adequately verified
- Received any disallowed concomitant medication during open-label treatment period
- Developed withdrawal criteria but were not withdrawn

The potentially important protocol deviations will be identified shortly before database lock, either programmatically (e.g., inclusion/exclusion criteria violations) or through review of data listings (e.g., investigator comments, concomitant medications). Appropriate personnel (including, at a minimum, a medical director, and a biostatistician) will review the list of potential IPDs to identify which will be considered IPDs. The final list of IPDs will be documented and used to generate a data listing. The number and percentage of subjects with IPDs will be summarized by the categories above.

Listing of IPDs will be provided. In addition, subject inclusion and exclusion criteria will be provided.

### 7.4 Demographic and Other Baseline Characteristics

Demographic and baseline characteristics at Screening/Visit 1 from Protocol 093-045 or 093-046 will be summarized including age, gender, race, ethnicity, country, height, weight, and BMI (continuous and categorized as <18, 18-30, >30 kg/m^2), concomitant AEDs, country, region (US/Non-US), as well as disease conditions, will be summarized using descriptive statistics.

Demographic and baseline characteristics, Medical history, and Epilepsy history will be summarized for the ITT population.

Listing of demographic and baseline characteristic data, medical history, and epilepsy history will be provided.

### 7.5 Extent of Exposure and Compliance

The extent of exposure will be summarized descriptively: it will be calculated as the date of last reported dose minus the first dose date of 093-050 study, ignoring missing days plus 1. If the day of first dose of study drug is unknown, this will be set to the first dispensing date. If the day of last dose of study drug is unknown, then this will be set to the day of last contact.

Extent of exposure will be summarized by the following mean daily dose categories:

- ESL < 1000 mg
- ESL 1000 mg – <1400 mg

- ESL 1400 mg – <2000 mg
- ESL  $\geq$  2000 mg
- Total ESL

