**Duration of Exposure:**

The frequency of duration of exposure will be summarized using the following categories:

- 1-7 Days
- > 1-2 Weeks
- > 2-4 Weeks
- > 4-6 Weeks
- > 6-8 Weeks
- > 8-10 Weeks
- >10-12 Weeks
- > 12-14 Weeks
- > 14-16 Weeks
- > 16-18 Weeks
- > 18-20 Weeks
- > 20-26 Weeks
- > 26-52 Weeks
- > 52-104 Weeks
- > 104 Weeks (24 Months)

Subject-years of exposure will be calculated by summing the overall exposure for each subject within the dose group dividing by 365.25.

The number of tablets taken per subject will be summarized as a continuous variable. The total number of tablets taken will be determined by subtracting the total number of tablets returned and reported lost from the total number of tablets dispensed.

Continuous summaries of mean daily dose will also be presented. The mean daily dose level (mg) of ESL will be calculated as the total number of tablets taken within each treatment interval multiplied by the tablet strength, and then divided by the duration (in days) of treatment within the treatment interval. The overall mean daily dose will be calculated as the weighted average of the treatment intervals (i.e., the sum of the non-missing mean daily doses for each treatment interval multiplied by their respective number of days in the interval, divided by the total number of days in the

intervals with non-missing mean daily doses).

Descriptive statistics will be used to summarize percent compliance. Further, the number and percent of subjects that are <80%, 80-120% or >120% will be displayed.

Percent compliance will be derived as the number of tablets taken divided by the number of tablets that should have been taken, expressed as a percent.

Listing of subject treatment exposure and compliance will be provided. In addition, listing of study drug dosing and study drug accountability including number of tablets dispensed, returned, lost/missing, taken will be provided.

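### The top mean-daily-dose cut (2000 mg) is itself an assignable dose, so subjects held on 2000 mg are grouped with 1600 mg subjects or placed by tablet-count noise

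*SAP*

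**What the plan says.** SAP 7.5 states: "Extent of exposure will be summarized by the following mean daily dose categories". The bands are below 1000 mg, "ESL 1000 mg – <1400 mg", "ESL 1400 mg – <2000 mg", 2000 mg and above, and a total.

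Under Duration of Exposure, SAP 7.5 derives the mean daily dose from tablet counts. Tablets taken are those dispensed less those returned or reported lost. The overall mean weights each treatment interval by its days and leaves out intervals whose mean is missing. On person-time it says: "Subject-years of exposure will be calculated by summing the overall exposure for each subject within the dose group dividing by 365.25".

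SAP 3.1 sets the dosing that feeds these means: "Subjects who enter the present study will receive a starting dose of 1600 mg QD of eslicarbazepine acetate, orally for 1 week". The start for subjects "who had a dose reduction during participation in studies 093-045 or 093-046 will be 1200 mg and not 1600 mg". After that, "all dose increases or reductions should occur in steps of 400 mg and a minimum of 1 week must pass" between changes, within limits of 800 and 2400 mg once daily.

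**The concern.** Start doses of 1600 or 1200 mg, 400 mg steps and limits of 800 and 2400 mg give five levels: 800, 1200, 1600, 2000 and 2400 mg. A cut midway between two levels tolerates ordinary variation in tablet counts and the lead-in at the starting dose. A cut placed on a level does not. For a subject held at that level, a small deviation in either direction decides the band. The first week at a lower dose pulls the mean below the cut from the outset.

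The primary objective (SAP 2.1) is safety and tolerability of flexible dosing from 800 to 2400 mg. Adverse events are tabulated by study period (SAP 7.7.1), and no subgroup in SAP 6.5 is defined by dose. The banded exposure table is therefore the only planned summary that divides subject-years by dose. A reader would use it to judge how much experience lies at the upper doses. The Actual Monotherapy Used subgroup in SAP 6.5 also has exposure summaries, and the same issue arises there if the same bands are used.

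**Working it through.** The plan states no figure of its own on this point, so there is nothing to reproduce first. The inputs are the dosing rules of SAP 3.1 and the day-weighted mean of SAP 7.5.

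**1. Cuts against midpoints.** (800 + 1200)/2 = 1000; (1200 + 1600)/2 = 1400; (1600 + 2000)/2 = 1800; (2000 + 2400)/2 = 2200. The plan's cuts are 1000, 1400 and 2000. The first two are midpoints and the third is not.

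**2. Subject held on 2000 mg, dosing exactly as prescribed.** D is days on treatment.

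- 1600 mg start: (7 × 1600 + (D − 7) × 2000)/D = 2000 − 2800/D.
- 1200 mg start, fastest permitted rise: (7 × 1200 + 7 × 1600 + (D − 14) × 2000)/D = 2000 − 8400/D.

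| D (days) | Mean, 1600 mg start | Mean, 1200 mg start | Counted compliance needed to reach 2000 mg (1600 mg start) |
|---|---|---|---|
| 28 | 1900.0 | 1700.0 | 105.26% |
| 91 | 1969.2 | 1907.7 | 101.56% |
| 182 | 1984.6 | 1953.8 | 100.78% |
| 365 | 1992.3 | 1977.0 | 100.39% |
| 730 | 1996.2 | 1988.5 | 100.19% |
| 1826 | 1998.5 | 1995.4 | 100.08% |

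Both means stay below 2000 mg for every finite D.

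**3. How little moves the subject.** At day 365 the prescribed total is 7 × 1600 + 358 × 2000 = 727,200 mg. A mean of 2000 mg needs 365 × 2000 = 730,000 mg. The gap is 2800 mg, which is 2800/727,200 = 0.39%, or 2800/2000 = 1.4 days of dosing. Counted compliance of 99% gives 0.99 × 1992.33 = 1972 mg; 101% gives 2012 mg. If the first-week interval is missing, the mean is (358 × 2000)/358 = 2000 mg exactly, and the subject is in the top band.

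Other levels have real margins. A steady 1200 mg subject stays in band from 1000/1200 = 83.3% to just under 1400/1200 = 116.7% counted compliance. A steady 1600 mg subject stays above 1400 mg down to 1400/1600 = 87.5%.

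**4. The opposite error.** Take 179 days at 1600 mg, 7 at 2000 mg and 179 at 2400 mg: (286,400 + 14,000 + 429,600)/365 = 730,000/365 = 2000 mg. All 365 days are credited to the top band, although 179 were at 1600 mg.

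**5. With a cut at 1800 mg.** Solving 2000 − 2800/D ≥ 1800 gives D ≥ 14; 2000 − 8400/D ≥ 1800 gives D ≥ 42. So, with full compliance, a subject kept on 2000 mg enters the upper band from day 14 or day 42. At day 365 the 1600 mg starter remains there down to 1800/1992.33 = 90.3% counted compliance. A steady 1600 mg subject would need 1800/1600 = 112.5% to cross.

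**The case against.** The bands are labelled as mean daily dose, not assigned dose. A mean of 1992 mg belongs below 2000 mg, so the table is correct as labelled. No section says the bands must represent dose levels or sit at midpoints; that is inferred from two of the three cuts. This is fair. The complaint is about what the table can tell a reader, not about arithmetic.

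A reader might infer that a subject kept on 2000 mg always falls below the cut. The documents do not support that. Tablets neither returned nor reported lost count as taken, a compliance category above 120% is provided for, and missing intervals drop out. Any of these can lift the subject over the cut. This weakens the word always, but it strengthens the case that noise decides placement.

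A reader might also infer that exposure at 2000 mg and above is understated overall. That is not shown. Crediting a subject's whole exposure to one band also carries lower-dose days of 2400 mg subjects into the top band (step 4), and the documents give no dose distribution.

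Nor is a 2400 mg subject with low compliance misclassified. The path 1600, 2000, then 2400 mg averages (11,200 + 14,000 + 842,400)/365 = 2377 mg at one year and falls below 2000 mg only under 2000/2377 = 84.1% compliance. Such a subject really did take less than 2000 mg a day. The 80–120% compliance range is a display category, not an acceptance range.

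Finally, any cut on an averaged flexible dose blurs some subjects. With an 1800 mg cut, three quarters of the time at 1600 mg and one quarter at 2400 mg averages 1800 mg and joins the upper band. That is true, but an 1800 mg cut does not sit on a dose at which subjects can be held.

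**Conclusion.** The point holds in a limited form. Relative to dose level, the exposure of subjects held on 2000 mg is misclassified. Under exact dosing all of it goes to the band shared with 1600 mg subjects, with a mean of 1992.3 mg at one year (about 1977 mg from a 1200 mg start). About 0.4% of excess in the count, or a missing first interval, sends all of it to the top band. The net effect on the top band is unknown.

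This rests on three assumptions: that the bands use the overall mean daily dose rather than an interval mean (SAP 7.5 defines both and does not say which); that tablet counts are complete; and that means are not rounded before banding. No rounding rule is stated. Rounding to the nearest 100 mg would give 2000 mg once 2800/D ≤ 50, that is, from day 56.

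The consequence is confined to descriptive exposure tables. No adverse event, laboratory or ECG summary is specified by these bands. The continuous mean-dose summaries and the dosing listing in SAP 7.5 mitigate part of the problem, but neither gives subject-years by dose level. The cut should be changed, but no safety or efficacy result depends on it.

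**What to change.** In SAP 7.5, place the third cut at the midpoint, as for the other two: *ESL 1400 mg – <1800 mg* and *ESL ≥ 1800 mg*. Preferably divide the latter at 2200 mg so that 2000 and 2400 mg are reported separately. Recompute subject counts and subject-years on these bands, and use the same bands for the Actual Monotherapy Used subgroup if its exposure is banded. State in the same place that banding uses the overall mean daily dose, and whether it is rounded first.

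This is a reporting change only; it does not touch dosing. It costs a line or two of SAP wording and one table layout, with no new data. The drawback is that the bands would no longer match any earlier exposure table that used 2000 mg. If that comparison matters, show both versions.
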